- LFTs $> 5x$ upper limit of normal or known cirrhosis
- Platelets less than 100,000 per cubic mm
- Acute condition at the time of enrollment that necessitates medical therapy with opioids
- Pregnant
- Incarcerated

Management of acute alcohol withdrawal:

XR-NTX is not a treatment for acute alcohol withdrawal. Acute alcohol withdrawal management will be left to the discretion of the treating physician.

Patients admitted to the hospital:

Hospital admission will not exclude an individual from study participation. The study medication will be delivered in the ED and the research case manager will follow the patient while he/she is an inpatient, and coordinate a follow-up plan with the admitting team at the time of hospital discharge.

III. Safety:

Adverse Events:

Serious adverse events have been reported to occur in $\sim 5\%$ of those treated with XR-NTX, which is similar to placebo [15]. Adverse events tend to be mild or moderate, with injection site pain, nausea, headache and fatigue being the most frequent.

The research case manager will collect information about adverse events at each monthly follow up visit and enter the data into RedCap data collection forms. Any unanticipated problems related to the study activities identified by the research team will be entered into the RedCap form as well. This data will be reviewed quarterly by the PI, who will determine if the event was expected, the severity of the event, and the likelihood that the event was related to the research study activities. Any serious adverse events will be reported to the PI immediately by the

research case manager, or any member of the research team who identifies a serious adverse event. The PI will report all serious adverse events resulting in death or possible life threatening events to the UCSF IRB immediately. All other adverse and unexpected events will be reported using the iRIS adverse event reporting forms within 5 business days of the PI becoming aware of the event.

Risks and risk minimization strategy:

Injection site pain, mild swelling, and possible ecchymosis are possible. The smallest acceptable needle size will be used and patients will be treated with non-narcotic oral analgesics as needed for bothersome injection site pain

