Because this is a feasibility study, primary outcomes of interest are recruitment (consent) rate, time required to complete initial tele-medicine assessment in the ED, time needed to administer XR-NTX in the ED, total ED length of stay, time to first follow up after the initial ED encounter, number of cell phones issued by the study, retention and follow up rates over the 3-month study

period, retention rate with other providers in San Francisco, number of doses of XR-NTX received during the study period and intervals between doses, and barriers to and facilitators of follow-up after the initial ED visit.

We will also collect pilot data on the following for statistical analysis:

Predictor Variable: Multi-modal treatment with Extended Release Naltrexone and case management

Primary Outcome: Change in the number of Emergency Department visits for alcohol-related complaints. [(# of ED visits for alcohol related complaint in 12 months after enrollment) - (# of ED visits for alcohol related complaint in 12 months before enrollment)].

Secondary Outcomes: number of standard alcoholic drinks consumed per week, number of days of heavy drinking, overall substance use severity (change in AUDIT score), change in alcohol-related social/occupational/psychological problems identified on SIP-2R, change in PEth, and change in urine ethyl glucuronide

Cost analysis: This study will not provide precise estimates of efficacy or costs. However, we will use our results to perform a basic cost analysis to guide future research. We will estimate: overall cost and cost per patient (medications, case management, follow-up visits), cost per avoided ED visit, cost per avoided hospitalization, program cost vs expected medical cost saved. All costs will be estimated at the societal perspective

Potential confounding variables or covariates, justifications:

There are several potential confounders which we will measure such as number of doses of XR-NTX received, willingness to change, engagement in other, baseline substance use severity, housing status, psychiatric and medical comorbidity, and basic demographic variables such as age and sex. The primary strategy employed to combat these cofounders is the selection of the primary outcome. Since the outcome is a change from the patient's baseline ED usage from the prior year each patient serves as their own control. Thus they are matched for many of the possible confounders.

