The risk of bias is substantial given that all enrollees are to be treated with XR-NRT and the study is not randomized or blinded and the population of interest is at high risk of being lost to follow up. We intend to conduct both an intention to treat analysis and a per protocol analysis, though our sample size may limit the utility of this approach. We will employ an independent data analyst to collect the ED visit counts and perform the final statistical analysis.

Statistical issues:

Statistical Test: Paired T Test

Hypothesis:

ED initiated Treatment of alcohol use disorders with multi-modal therapy reduces alcohol related ED visits in patients with frequent ED visits for alcohol related complaints

Sample Size:

We will enroll 25 patients. As a feasibility study our sample size was chosen as it represents a reasonable patient load for a single case manager. Because this population is difficult to retain in treatment, we anticipate the drop-out rate will be significant. Patients who drop out of the study (either withdraw or are lost to follow up) will be replaced with new enrollees until 25 patients have been recruited into the study. The goal of this practice is to maximize the benefit to the patient population, avoid wasting donated study medication, and to allow the research team to optimize recruitment and retention strategies.

Last year 42 patients presented to the UCSF Emergency Department at least 4 times for an alcohol related complaint. Of this group the mean number of visits was 8.49 with a SD of 8.58. The median number of visits was 6. The number of visits ranged from 4-47. After excluding 2 outliers (40 and 47 visits, each $> 3SD$ above the mean) the mean was 6.78 visits with a SD of 3.5 visits.

We estimate a standardized effect size of 0.584 would represent 2-5 emergency visits for alcohol related complaints. This equates to a 29-59% reduction in ED utilization, which is clinically relevant.

Data management plan:

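### The pilot Primary Outcome subtracts raw 12-month visit counts with no allowance for time at risk, so a death after enrolment is scored as fewer ED visits

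*Combined protocol and SAP*

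**What the plan says.** Section IV (Analysis, Measurements, and Outcomes) defines the pilot Primary Outcome as a difference of two counts: the number "of ED visits for alcohol related complaint in 12 months after enrollment" less the number "of ED visits for alcohol related complaint in 12 months before enrollment". Under Statistical issues the analysis is given as "Statistical Test: Paired T Test". Neither place has a person-time denominator, an annualised rate, a censoring rule or a rule for death.

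The surrounding text bears on this in five ways:

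- **Source of the count.** Under Follow up procedures after visit 3, outcome data are completed by a closing review of the hospital record and the shared ED exchange (EDIE). Initial Screening describes EDIE as covering UCSF, San Francisco General and several other Bay Area departments.
- **Custody.** "Incarcerated" appears in the Exclusion Criteria and so applies at entry. Nothing is said about custody afterwards.
- **Attrition.** Section IV concedes that "the population of interest is at high risk of being lost to follow up". Patients who withdraw or are lost are replaced. The text does not say whether their counts stay in the analysis, and it does not name death or custody.
- **Analysis sets.** Intention-to-treat and per-protocol analyses are both planned, and neither is defined.
- **Export.** The Data management plan sends no dates to the statistical package.

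**The concern.** The design's main defence against confounding is that each patient is their own control. That works only if the two windows offer the same opportunity to be seen in an ED. The before window is fully survived by construction. The after window may not be. Because the count comes from a record search, a patient who has died generates no records, and the formula reads the silence as avoided visits.

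The 12 calendar months have elapsed for such a patient, so waiting for full calendar follow-up would not remove the problem. The error favours the stated hypothesis, and it enters the planned cost per avoided ED visit as well.

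**Working it through.** **Inputs (Sample Size, section IV).** "We will enroll 25 patients". For all 42 frequent attenders, "the mean number of visits was 8.49 with a SD of 8.58"; after two outliers are removed, the mean is 6.78 and the SD 3.5. "We estimate a standardized effect size of 0.584 would represent 2-5 emergency visits for alcohol related complaints", described as a 29-59% reduction. Alpha, sidedness and power are not stated. Nor is any rate of death, custody or relocation.

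**Step 1: reproduce the plan's figure.** A paired t test with n = 25, two-sided alpha 0.05 and 80% power (both assumed) has noncentrality 0.584 × √25 = 2.92 on 24 degrees of freedom and power 79.996%, so 0.584 reproduces. In visits:

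- outliers excluded: 0.584 × 3.5 = 2.04 (2.04/6.78 = 30.1%; 2/6.78 = 29.5%)
- all patients: 0.584 × 8.58 = 5.01 (5.01/8.49 = 59.0%)

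The effect of 2.04 therefore belongs with the mean of 6.78, and 5.01 with 8.49.

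**Step 2: one patient.** Death at month 3 with an unchanged rate gives an expected change of -(9/12) × 6.78 = -5.09 visits, or -(9/12) × 8.49 = -6.37. The true change in rate is zero.

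**Step 3: the mean.** If k of 25 analysed patients leave observation at month m and treatment has no effect:

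shift = -(k/25) × (1 - m/12) × baseline mean

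| Exit month | k | Mean 6.78 | Share of 2.04 | Mean 8.49 | Share of 5.01 |
|---|---|---|---|---|---|
| 3 | 2 | -0.41 | 20% | -0.51 | 10% |
| 3 | 4 | -0.81 | 40% | -1.02 | 20% |
| 6 | 2 | -0.27 | 13% | -0.34 | 7% |
| 6 | 4 | -0.54 | 27% | -0.68 | 14% |

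To imitate the whole planned effect, the after window would have to lose 30% (2.04/6.78) to 59% (5.01/8.49) of its person-time.

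**Step 4: the test.** Counts were simulated from a gamma-Poisson model matched to each stated mean and SD, with stable underlying rates, no treatment effect and 40,000 runs. The nominal chance of a significant reduction is 2.5%.

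| Patients losing 6 months | Raw difference | After count divided by time at risk |
|---|---|---|
| 2 of 25 | 4.5-5.0% | 2.3-2.7% |
| 5 of 25 | 10.8-11.8% | 2.4-2.5% |

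**The case against.** **This is a feasibility study.** Its lead outcomes are feasibility measures, the visit counts are called pilot data, precise estimates of efficacy or cost are disclaimed, and substantial bias is admitted. All of this limits the consequences. It does not change the fact that this is the labelled Primary Outcome, with a hypothesis and a test, ahead of a planned randomised trial. The general admission of bias corrects nothing here.

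**A reader might infer that death, custody and moving away all push the same way.** Only death does so with certainty. The custody exclusion applies at enrolment, so a patient may have been in custody, or outside coverage, earlier in the before year. That lowers the before count and works against the hypothesis. A net excess afterwards is plausible, but no figure supports it. A move matters only if it leaves EDIE coverage, and the roughly monthly calls may pick up some outside visits.

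**A reader might also put the bias at 25-50% of the planned effect,** from 0.51/2.04 and 1.02/2.04. That divides shifts built on the full-sample mean by the effect from the outlier-excluded sample. Matched pairs give 10-40% for exits at month 3.

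**Replacement of dropouts may change who is counted.** This stands, and it makes k of 25 an assumption in itself. If leavers stay in the analysis in addition to 25 retained patients, each weighs less. Two leavers at month 3 give (2/27) × 0.75 × 6.78 = 0.38, or 0.47 with 8.49. Four give (4/29) × 0.75 × 6.78 = 0.70, or 0.88. If leavers are instead dropped, this bias is exchanged for selection on retention.

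**Conclusion.** The point holds as a defect in a stated rule: followed exactly, the plan scores a death after enrolment as avoided ED visits. For death the direction is certain. For known custody and for leaving EDIE coverage it is plausible only.

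The size rests on assumed exits, no treatment effect, an unchanged visit rate and 25 analysed patients. With 2 or 4 exits, the shift is 10-40% of the planned effect at month 3 and 7-27% at month 6. These losses are not enough to produce the planned effect alone, but they are enough to roughly double the chance of a false reduction (2 of 25 losing six months) or raise it more than fourfold (5 of 25). The outcome should be redefined before the analysis file is built.

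**What to change.** 1. Record the date and reason for leaving observation: death, and custody or leaving EDIE coverage where known. The follow-up sections list ED and inpatient use, substance use, readiness to change, treatment engagement and doses. They do not list these items, so new fields are needed.
2. Create a days-at-risk variable for each window before export, because no dates reach the analyst.
3. Make the lead analysis visits per unit time at risk, using a paired count model with a log person-time offset so that a very short follow-up does not get full weight. State that this estimates a rate while observed.
4. Keep patients with shortened observation in the intention-to-treat set, and report deaths and months lost.
5. Add a sensitivity analysis that fills lost months at the patient's own pre-enrolment rate. Keep the raw paired difference as supportive.

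Custody or relocation that nobody learns of will still go uncorrected, and the report should say so.

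The cost is a few data fields, a change of lead analysis from the paired t test, and possibly a less favourable estimate. Label: cheap improvement.

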This is a phase 4 open label feasibility study of extended release naltrexone (Vivitrol, Alkermes Pharmaceutical), case management and tele-addiction medicine for treatment of alcohol use disorders in the ED. The planned study period is 2 years. During this time we will conduct necessary department staff training and recruit 25 patients. Each patient will be followed for 12 months from index visit by our study staff, with case management provided by a full-time research case manager. Patients will be enrolled consecutively, 24 hours a day, 7 days a week. Recruitment will take place in the UCSF Emergency Department, Parnassus campus. Follow up visits may occur in the UCSF ED or an outpatient setting agreed upon by the patient and the research case manager. Patients who drop out of the study will be replaced with new patients; enrollment will end once 25 patients have been retained in the study or at the planned end date.

Initial Screening:

All adult patients presenting to the University of California San Francisco ED during the study period will be screened for frequent ED utilization (defined as 3 or more ED visits in the past 12 months including the index visit) by electronic medical record review conducted by the treating physician or member of the research team. UCSF, San Francisco General, and several other academic and community emergency departments in the San Francisco Bay Area share an electronic platform called the Emergency Department Information Exchange, or EDIE, that documents dates of ED visits and diagnoses. UC emergency providers can view visits at each of these sites, and ED visits to any hospital will be counted towards this 3-or-more threshold.

Determination of Eligibility:

An ED provider or staff (including physicians, advanced health practitioners, nurses, social workers, and case managers) may alert the PI or research study staff of potentially eligible patients based on the initial screen. The research team member will then determine eligibility as described below.

The PI [name], research fellow [name] or study staff (the research case manager) can all determine study eligibility. Initial eligibility will be determined based on chart review during the time of an ED visit. During study hours, the above mentioned faculty and staff will examine the

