The UBACC is a validated 10-item questionnaire used previously in this population [16,17]. It rates the basic elements of capacity (understanding, appreciation, reasoning, and ability to express a choice) to identify subjects with questionable capacity to consent to a specified research project. Administration of the UBACC will occur after informing the patient about the study. The consenter will review each page of the informed consent document with the patient, pausing to reassess comprehension throughout the process. Then they will administer the UBACC. Once the patient's understanding is confirmed by the UBACC, the consenter will request the patient's signature and provide the patient with a copy of the signed consent document. If the consenter doubts the patient's comprehension of the study procedures the patient will not be enrolled at that time, but may be eligible in the future. Once capacity is established the patient will be asked to provide informed consent.

Consent:

Patients deemed to be eligible for enrollment after electronic record review may be approached by a member of the research team to assess willingness to participate. For patients interested in participating consent will occur only after the patient is clinically sober as judged by the treating ED provider and their capacity to consent has been established by the consenter, using the UBACC if necessary. The consenter will provide patients with information about the study, including risks and benefits of treatment with extended release naltrexone both verbally and in print. If the patient wishes to enroll in the study they will be consented by a member of the research team (research case manager, PI, research fellow) and sign the consent document.

With the exception of the research case manager, all members of the research team are practicing Emergency Medicine Physicians who frequently obtain informed consent for a variety of procedures performed while caring for patients in the emergency department and have completed required human subjects research training.

The research case manager will be trained in obtaining informed consent by completing the required training modules for UCSF human subjects researchers and be trained in the teach back method and use of the UBACC by the study PI, [name].

Enrollment:

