Following completion of the 3rd injection visit the patient will no longer receive XR-Naltrexone through the study. They will be encouraged to continue engaging with other community health providers to continue treatment, but are not required to do so. During the 9 months after the final injection visit the patient will contacted by phone approximately once a month by a member of the research team to collect outcome data as well as to discuss any ongoing treatment or changes in their health that occurred after the completion of the treatment period. At the end of the 12 month study period a data analyst will conduct a final review of the EHR and EDIE network to complete the collection of outcome data.

Case management services between study visits 1-3:

Between injection visits, the research case manager will be available to participants to assist with their needs including being connected to longer term case management services, connection with a primary care provider, or other services they may need related to food, clothing, and shelter. If participants who have chosen to follow up with community providers are having difficulty

making appointment, for example because they cannot find transportation, the research case manager can facilitate transportation to appointment. Participants can also choose to switch from following up in the UCSF ED to community providers of XR-NTX at any time. In such cases, the research case manager will coordinate referral to an alternative provider in San Francisco who can administer XR-NTX. Participants will be able to contact the study case manager by phone or meet in person depending on the case manager's availability.

Transition to ongoing care:

Patients who wishes to receive treatment with XR-Naltrexone after completing their 3 injections or after dropping out of the study will have the following options:

1. If the patient has been receiving injections during the study from a community provider they may continue treatment after the 3rd injection or choosing to drop out of the study.
2. If the patient has been receiving injections during the study in the UCSF ED they can be referred to a community site that administers XR-Naltrexone to establish treatment.

Handling of missed injection visits:

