Patients who miss scheduled follow up injection visits will be contacted and asked to reschedule their injection visit as soon as possible. If they are able to reschedule within 2 weeks then no changes to study procedure are necessary. If they are able to reschedule within 2-4 weeks then they will be asked if they have used any opiates (including fentanyl) in the past 7 days. If they have not used opiates in the past 7 days then they will resume treatment, provided they are not endorsing any signs or symptoms of liver injury. If they endorse signs or symptoms of liver injury they will undergo screening as outlined above. If they endorse using opiates then they will not be allowed to resume treatment through the study. If a patient is unable to reschedule a missed injection appointment within one month they will not be allowed to continue in the study. If a patient is unable to resume treatment through the study then they will be provided with alternative follow up options (see transition to ongoing care).

Participant Payment:

A 20-dollar gift card incentive will be used to encourage attendance at the 6 monthly follow up visits required for XR-Naltrexone injections. Gift cards will be given at each of the six visits. The total value of gift cards available to each participant during the study period is \$120.00. Gift cards will be issued for locations that do not sell alcohol (e.g. Starbucks coffee).

Study Subjects:

The target population is patients with frequent ED visits for alcohol related complaints who may benefit from ED-initiated XR-NTX. The accessible population is all people in the San Francisco Bay Area presenting to the ED with an alcohol related complaint. The study sample will be adult

patients presenting to the UCSF ED with active hazardous or high risk alcohol use and ≥ 4 ED visits in the past 12 months for alcohol related complaints.

Inclusion Criteria:

- Age ≥ 21
- AUDIT score ≥ 8
- Frequent emergency department visits, defined as: At least 3 emergency department visits for in the past 12 months, including the index visit.

Exclusion Criteria:

- Opioid use: currently receiving opioid analgesics, self-report of opioid use in past 7 days, current physiologic opioid dependence, patients in acute opioid withdrawal, urine toxicology screen positive for opiates including fentanyl
- History of hypersensitivity to naltrexone, polylactide-co-glycolide (PLG), carboxymethylcellulose, or any other components of the diluent

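### The ED visit at which each patient is enrolled is not excluded from the change score; read in time order it counts only in the 'before' year and biases the mean change toward a reduction

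*Combined protocol and SAP*

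**What the plan says.** Section IV, Primary Outcome, defines the change as alcohol-related ED visits in the year after enrollment minus the number "of ED visits for alcohol related complaint in 12 months before enrollment". The test is a paired t test, with the hypothesis that treatment reduces such visits (Statistical issues). The defence against confounding is that "each patient serves as their own control" (Potential confounding variables).

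Enrollment takes place inside an ED visit. Under Section II the patient has arrived, had the chart reviewed and been approached, and "consent will occur only after the patient is clinically sober as judged by the treating ED provider" (Consent); AUDIT screening and laboratory criteria also precede enrollment (Enrollment). Overview of Design sets the follow-up clock differently: "Each patient will be followed for 12 months from index visit by our study staff".

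The outcome definition is silent on the index visit. The only look-back that mentions it is the eligibility count, which includes it (Initial Screening; Inclusion Criteria).

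The counts come from records. Initial Screening describes the shared ED platform as one "that documents dates of ED visits and diagnoses". At 12 months "a data analyst will conduct a final review of the EHR and EDIE network to complete the collection of outcome data" (Follow up procedures after visit 3), and Section IV adds: "We will employ an independent data analyst to collect the ED visit counts and perform the final statistical analysis".

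**The concern.** Every participant has an index visit, because that is where recruitment happens. By the time of enrollment that visit has already begun, so in time order it belongs to 'before'. Nothing guarantees a matching visit in 'after'. A patient whose underlying visit rate never changes would therefore show an apparent fall.

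The paired t test compares the mean change with zero, and no comparison arm shares the extra visit and removes it. The shift points the same way as the hypothesis. The plan also intends a cost per avoided ED visit to guide later research, and its timeline ends with a proposal for a randomized trial, so an inflated pilot effect could be carried forward.

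**Working it through.** **Inputs from the plan (Section IV, Sample Size).** n = 25; standardized effect 0.584, said to represent 2-5 visits or a 29-59% reduction; mean 8.49 and SD 8.58 in all 42 patients; mean 6.78 and SD 3.5 after removing two outliers.

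**Assumed, because not stated.** Two-sided alpha 5%; the SD of the change; q.

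**1. The plan's own figure.** For a paired t test with n = 25, df = 24, two-sided 5% and 80% power, the noncentral t distribution gives a detectable effect of 0.584, matching the plan. In visits: 0.584 x 3.5 = 2.04 (30% of 6.78; the rounded 2 visits is 29%), and 0.584 x 8.58 = 5.01 (59% of 8.49).

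**2. The index-visit component.** Let L be a patient's stable yearly rate of alcohol-related ED visits, with no treatment effect and ignoring selection on past visits.

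- Index visit in 'before': E[before] = L + q and E[after] = L, so E[change] = -q.
- Index visit in neither window: E[change] = L - L = 0.

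On q, Study Subjects says "The accessible population is all people in the San Francisco Bay Area presenting to the ED with an alcohol related complaint", which suggests a value near 1. The inclusion criteria do not require an alcohol-related index visit, so q can lie anywhere from 0 to 1.

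**3. Size against the targets, q = 1.** 1/2.04 = 49%; 1/5.01 = 20%.

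**4. Rejection with no treatment effect.** The noncentrality is q x sqrt(25)/SD, with df = 24 and critical value 2.064. The plan gives only between-patient SDs, so a range is shown. The rows 3.68 = sqrt(2 x 6.78) and 4.12 = sqrt(2 x 8.49) are the SDs of change that Poisson variation alone would give at the plan's two means with stable rates.

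| Assumed SD of change | q = 1 | q = 0.5 |
|---|---|---|
| 3.5 | 27.9% | 10.5% |
| 3.68 | 25.6% | 10.0% |
| 4.12 | 21.4% | 9.0% |
| 5 | 16.1% | 7.7% |
| 8.58 | 8.7% | 5.9% |

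The nominal figure is 5%. At SD 3.5 and q = 1, 27.8 of the 27.9 percentage points are rejections in favour of treatment.

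**5. Selection on recent visits.** Simulated no-effect changes used Poisson visits at assumed mean rates of 3 to 8.5 per year (fixed or gamma-distributed), all alcohol-related, with patients met in proportion to their visit rate.

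| Entry threshold | Index visit in 'before' | Index visit in neither |
|---|---|---|
| None | -0.98 to -1.01 | -0.01 to +0.02 |
| 3 visits | -1.02 to -1.56 | -0.02 to -0.56 |
| 4 visits | -1.06 to -2.17 | -0.06 to -1.17 |

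Both thresholds are shown because the plan gives 3 in Inclusion Criteria and 4 in Determination of Eligibility and Study Subjects. Excluding the index visit removes one whole visit in each case; what remains is regression to the mean and depends on the model.

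**6. Cost per avoided visit, only if it uses these counts.** For a true fall of T visits, the figure is too low by 1 - T/(T + q). T = 2: 20% (q = 0.5) and 33% (q = 1). T = 5: 9% and 17%.

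**The case against.** The strongest reply is that this is silence, not a stated error. Section IV speaks of baseline use in the prior year, and follow-up runs from the index visit. Both fit an index visit at time zero counted in neither window, which gives no shift. Where the authors want the index visit counted, in the eligibility rule, they say so. That reading is possible, and a reader should not infer that the plan places the visit in 'before' explicitly. But the outcome is anchored on enrollment, enrollment follows arrival, and no text takes the visit out.

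The net direction is also uncertain. Injections may be given in the UCSF ED, and arranged liver checks take place there. If injection visits 2 and 3 were coded as alcohol-related, they could add up to two visits to 'after' and offset or reverse the shift. This stands, and it is a second undefined count rather than a safeguard.

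The rejection rates are illustrative. The 3.5 is a between-patient SD after outlier removal and lies slightly below the Poisson figure of 3.68. The planning cohort had at least 4 alcohol-related UCSF visits, whereas inclusion needs 3 ED visits at any hospital, so its means and SDs may not transfer.

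Finally, the plan puts feasibility outcomes first, calls these pilot data, disclaims precise estimates of efficacy or cost, and admits substantial risk of bias. That limits the consequence. It does not justify keeping a component that a definition removes, in an outcome the plan does test.

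**Conclusion.** The point holds as a gap in the outcome definition that, followed in time order, shifts the mean change by -q visits in favour of treatment. At q = 1 that is about half of the lower target and a fifth of the upper one, with no-effect rejection of roughly 9% to 28%; at q = 0.5 it is roughly 6% to 10%. These figures assume a two-sided 5% test, an SD of change between 8.58 and 3.5, and stable visit rates. It should be fixed before the counts are collected. It does not affect N, which rests on case-manager load.

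Three stronger inferences are not supported:

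- That one visit is the most the no-effect change can be. The -q is only the index-visit component; selection by visit threshold and the way patients are sampled can make the total larger.
- That a tie between index and enrollment dates could put the visit in 'after', so that two analysts differ by two visits. The plan states no such tie rule, and time order rules it out.
- That a strong before-after correlation justifies rejection rates well above 28%. That needs an SD of change well below what Poisson variation alone gives at the plan's means.

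**What to change.** In Section IV, Primary Outcome, define 'before' as the 12 months ending just before arrival at the index ED visit and 'after' as the 12 months starting at ED discharge from that visit, with the index encounter in neither. Have the independent analyst flag that encounter and leave it out when the counts are collected. This must happen at the data pull, because the Data management plan says that dates are not exported to the analysis file.

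State also that ED encounters made solely for a study injection or an arranged study liver check are not alcohol-related visits, since counting them would bias 'after' upward. List regression to the mean from selecting on recent visits as a remaining limitation. If the cost per avoided visit uses these counts, apply the same windows there.

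The cost is a few sentences and one flag per patient, with no extra patients, visits or data. The downside is that the observed reduction may look up to one visit smaller than if the index visit were counted in 'before'.
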